## Appendix O(a) : Flipchart for mothers' on Kangaroo Care (English version)

 **UNIVERSITI  
MALAYA**  
KUALA LUMPUR  
PUSAT PERUBATAN UM

 **UNIVERSITY  
OF MALAYA**

## Outline objectives

1. **WHAT** is Kangaroo Care?
2. **HOW** do I perform Kangaroo Care?
3. **WHY** should I perform Kangaroo Care?
  - 3.1 For babies;
  - 3.2 For mothers;
4. **WHO** can perform Kangaroo Care?
5. **WHEN** can I perform Kangaroo Care?

2

 **Kangaroo**  

3

## WHAT is kangaroo care?

- ❖ It's a **special way** and **method of caring for a premature** baby in which the baby is positioned in an **upright** skin-to-skin and **chest-to-chest** contact with a mother for at **least 1 hour per day**. Moms initiate it in the Neonatal Intensive Care Unit (NICU) and **continue at home** until the first **3 months old**.

Ludington-Hoe, et al., (1990, 2013, 2018)

[figure not shown]
## WHEN can I perform Kangaroo Care?

- ❖ Any time can work at **90 to 120 minutes post feeding**. Plan a convenient period with your nurse and set aside at least **1 hour or 60 minutes per day** and continuously **7 hours in a week** to sit with your baby.

For more information, please feel free to ask a member of NICU team.

## Special Care Nursery University Malaya Medical Centre Kangaroo Care Workshop

**Kangaroo Care Workshop**

A collage of four photographs showing a Kangaroo Care workshop. The top-left photo shows a group of people in a room with a kangaroo logo on the wall. The other three photos show nurses in green scrubs and headscarves interacting with babies in a hospital setting, demonstrating the Kangaroo Care technique.

**Doctors & nurses are trained in caring the mother and baby for kangaroo care**

A collage of six photographs showing medical professionals, including doctors and nurses, in a hospital setting. They are wearing scrubs and headscarves, and are seen holding and caring for babies, demonstrating the Kangaroo Care technique.

**Evidenced by Kangaroo Care practice**

- ❖ Evidence shows that **visitation, holding, talking, and skin to skin contact** are associated with better outcomes for infants and parents during hospitalization and beyond.

Feeley.N., Genest.C., Niela-Vilin.H., Charbonneau.L., & Axelin.A. (2016)

- ❖ Kangaroo care **improves cerebral blood flow (CBF)**, thus it might influence the structure and **promote development** of the **premature infant's brain**.

Koraa. A. El Nagger. A. Mohamed. R., & Helmy.N. (2014)

## Cont.

- Kangaroo care can be used to **promote emotional bonding** and **support between mothers and their babies**, and to **stabilize the physiological functions** of premature babies and may be one of **the most effective nursing interventions** in the neonatal intensive care unit **for the care of preterm infants and their mothers.**

Cho E,et al.,(2016)

11

## The Use Of Kangaroo Care Is Spreading Around The World

- It started in **Bogota, Colombia** approximately **30 years ago**
- **KC In Africa** - Benin, Burkina Faso, Ethiopia, Mali and Malawi (WHO,2014)
- **KC In Asia** - India, Indonesia and the Philippines (Recent study,1990,2012)
- **KC In Europe** - Belgium, Denmark, France, Italy, the Netherlands, Spain, Sweden and the UK.(Spanish study report, 2013)

## Kangaroo Care world wide

12

## HOW do I perform Kangaroo Care?

- ❖ You will dress your baby only a **diaper** and **head cap**. Your baby should be placed in an **upright** position between your breasts. Have their **tummy** against your **chest**. Head turned to one side, arm and legs in **flexed position**. Support your baby's head, back and **buttocks**. (Ludington-Hoe, et al., [1990,2013,2018] & Nyquist, [2010])

Figure 1: Positioning of Kangaroo Care

37

38

## WHY should I perform Kangaroo Care?

- ❖ There are lots of benefits for babies and mother :-

### For babies;

- Improve babies' sleep which can **promote weight gain** and **brain development**.
- Regulates babies' **temperature**, **heart rate** and **breathing**.
- Supports **successful breast feeding** sessions and reduces infection.
- **Shortens** length of hospital stay.

## WHY should I perform Kangaroo Care?

### For mothers:

- Increases confidence in **ability to care** for babies.
- Enhanced **bonding**, feeling of **closeness** with babies.
- Improve mothers' **milk production**.
- Creates more **nurturing interactions**.

20

## Benefits of breastfeeding

## Top 10 benefits of breastfeeding

### Top Benefits of Breastfeeding for Mothers and Babies

### Colostrum

[figure not shown]
**Property**

- Antibody-rich
- Many white cells
- Purgative
- Growth factors
- Vitamin-A rich

**Importance**

- protects against infection and allergy
- protects against infection
- clears meconium; helps prevent jaundice
- helps intestine mature; prevents allergy, intolerance
- reduces severity of some infection (such as measles and diarrhoea); prevents vitamin A-related eye diseases

22

**Nursing & mother daily documentation**

Gestational Age Week 32/40	Kangaroo Care				Body Weight (kg)	Feeding	
	Pre Temp	Post Temp	Time Start	Time End		Types of feeding (✓)	
Thursday 26/7/2018	36.8°C	37.2°C	8.00am	9.00am	1.790 kg	Express Breast Milk	✓
						Breast Feeding	✓
						Formula Milk	
Friday 27/7/2018	37.0°C	37.3°C	2.00pm	3.00pm	1.800 kg	Express Breast Milk	✓
						Breast Feeding	✓
						Formula Milk	

28

## Appendix O(b) : Flipchart for mothers' (Malay version)

UNIVERSITI  
MALAYA  
KUALA LUMPUR  
PUSAT PERUBATAN UM

UNIVERSITY OF MALAYA

## Objektif

1. **APAKAH** Kangaroo Care?
2. **SIAPAKAH** boleh melakukan Kangaroo Care?
3. **BILAKAH** saya boleh melakukan Kangaroo Care?
4. **BAGAIMANAKAH** cara Kangaroo Care dilakukan?
5. **KENAPAKAH** Kangaroo Care perlu dilakukan?

2

Kangaroo

3

## APAKAH Kangaroo Care?

- Kangaroo Care adalah cara atau **kaedah yang khusus** untuk penjagaan bayi pramatang. Ia dilakukan dengan merapatkan **sentuhan kulit di bahagian dada ibu dan bayi** seperti kangaroo membawa bayinya di hadapan kantung. Di mana bayi bersentuhan dari kulit-ke-kulit dan **dada bayi ke dada ibu** secara menegak, sekurang-kurangnya **1 jam sehari**. Para ibu boleh memulakannya di Unit Rawatan Rapi Neonatal (NICU) dan diteruskan di rumah sehingga bayi berusia **3 bulan pertama**.

## SIAPAKAH boleh melakukan Kangaroo Care?

- Semua **ibu** boleh melakukan kaedah Kangaroo Care. Namun begitu, setiap kaedah perubatan di NICU adalah berbeza. Anda boleh **bertanya kepada jururawat** sekiranya bayi anda mampu menjadi **calon** yang baik. Para ibu tidak perlu merasa risau sekiranya tidak selesa ketika melakukan kaedah Kangaroo Care. Rujuk jururawat bertugas kerana mereka mempunyai pelbagai cara membantu penjagaan bayi.

## BILAKAH saya boleh melakukan Kangaroo Care?

- Kangaroo Care boleh dilakukan pada **bila-bila masa** diantara **90 - 120 minit** selepas menyusu. Ibu perlu berbincang dengan jururawat yang bertugas untuk berada bersama bayi sekurang-kurangnya **1 jam atau 60 minit** untuk sesuatu sesi Kangaroo Care, manakala **7 jam dalam masa 1 minggu**. Kaedah ini perlu **diteruskan** sehingga bayi anda berusia **3 bulan** pertama.

**Special Care Nursery  
University Malaya Medical Centre  
Kangaroo Care Workshop**

**Kangaroo Care Workshop**

**Doktor dan jururawat terlatih dalam menjaga ibu dan bayi dalam amalan Kangaroo Care**

## Fakta dan bukti amalan Kangaroo Care

- ❖ Bukti menunjukkan bahawa lawatan, memegang, bercakap, dan **sentuhan kulit ke kulit** dikaitkan dengan hasil yang lebih baik untuk bayi dan ibu bapa semasa dimasukkan ke hospital dan seterusnya.

Feeley,N., Genest,C., Niela-Vilin,H.,Charbonneau,L., & Axelin,A. (2016)

- ❖ Kangaroo care meningkatkan aliran darah serebrum (CBF), oleh itu ia mungkin mempengaruhi struktur dan mempromosikan **perkembangan otak bayi pramatang**.

30

## Sambungan

- ❖ Kangaroo care boleh digunakan untuk menggalakkan ikatan emosi dan sokongan antara ibu dan bayi, bagi menstabilkan fungsi fisiologi bayi pramatang dan mungkin merupakan salah **satu intervensi kejururawatan yang paling berkesan** dalam Unit Perawatan Rapi Neonatal (NICU) untuk penjagaan bayi pramatang dan ibu mereka.

Cho E,et al. (2016)

31

## Amalan Kangaroo Care di seluruh dunia.

- Ia bermula di **Bogota**, Colombia kira - kira **30 tahun** yang lalu.
- **KC di Afrika** - Benin,Burkina Faso, Ethiopia, Mali dan Malawi (WHO, 2014).
- **KC di Asia** - India,Indonesia dan Filipina. (Kajian terkini, 1990-2012)
- **KC di Eropah** - Belgium,Denmark, Perancis, Itali, Belanda, Sepanyol, Sweden dan Inggeris. (Kajian Sepanyol laporan, 2013)

Sejak 15 Mei 2011, "Hari Kesedaran Kangaroo Care" telah diperhatikan di seluruh dunia.

32

## Kangaroo Care di seluruh dunia.

13

14

## Shared Kangaroo Care

[figure not shown]

15

## BAGAIMANAKAH cara Kangaroo Care dilakukan?

- Kangaroo Care dilakukan dengan bayi dipakaikan **lampin** pakai **buang** dan **topi** sahaja.
- Bayi dirapatkan kebahagian dada ibu dalam keadaan **menegak** berada diantara payudara ibu.
- **Perut bayi bersentuhan dengan dada ibu.** Kepala bayi dihalakan ke satu arah, kaki dan tangan berada dalam **posisi membengkok** seperti katak.
- Ibu dikehendaki menyokong bahagian kepala,belakang dan punggung bayi.

Gambarajah 1 : Posisi Kangaroo Care

37

## KENAPAKAH saya perlu melakukan Kangaroo Care ?

- ❖ Terdapat banyak manfaat untuk ibu dan bayi.

### Untuk bayi;

- **Menyerupai persekitaran rahim** yang menenangkan.
- **Mengawal suhu badan**, kadar denyutan jantung dan pernafasan bayi supaya berada dalam keadaan **stabil**.

- Bayi **kurang menangis**.
- Meningkatkan tempoh **tidur yang lebih lama** (yang boleh menggalakkan pertumbuhan dan perkembangan keseluruhan).
- Meningkatkan pertambahan **berat badan**.
- Menyokong sesi penyusuan **susu ibu** sepenuhnya.
- Pelepasan **awal** dari hospital.

19

## KENAPAKAH saya perlu melakukan Kangaroo Care?

### Untuk ibu;

- **Meningkatkan** penghasilan dan **pengeluaran susu ibu**.
- Menggeratkan **kasih sayang** antara ibu dan bayi.
- **Membina keyakinan** ibu menjaga bayi pramatang.
- **Mengurangkan tekanan** dan rasa dihargai.

20

## Kelebihan

### Susu Ibu

**KEBAIKKAN KEPADA BAYI**

- 1. **ZAT PEMAKANAN**  
Mengandungi zat pemakanan yang betul, yang diperlukan oleh bayi semasa dalam pertumbuhannya.
- 2. **ANTIBODI**  
Susu ibu mempunyai antibodi semulajadi untuk bayi yang boleh melindungi bayi dari jangkitan.
- 3. **MENCEGAH JANGKITAN**  
Bayi yang menyusu dengan ibunya jarang mendapat jangkitan seperti cinti-birit, jangkitan saluran pernafasan dan juga radang paru-paru.
- 4. **MENCEGAH BAYI DARI ALAHAN**  
Susu ibu dapat mengurangi bayi dari mendapat alahan.
- 5. **KURANG PENCEMARAN**  
Susu ibu diberi terus melalui putih susu dan terus kedalaman mulut bayi. Cara ini tidak mendedahkan air susu itu dicemari oleh udara.
- 6. **SUHU**  
Susu susu ibu amat sesuai untuk bayi. Dengan ini ibu tidak perlu khusul tentang tahap kepanasan atau sejuk susu ibu.
- 7. **JIMAT MASA**  
Penyusuan susu ibu tidak perlu masa untuk menyediakannya. Ianya boleh di berikan pada bila-bila masa.
- 8. **MUDAH DIJADAMAN**  
Susu ibu amat sesuai untuk bayi kerana ia mudah di hadamkan.

**KEBAIKKAN KEPADA IBU**

- 1. **MUDAH**  
Susu ibu senang diberi. Ianya boleh dilakukan di mana-mana pada bila-bila masa.
- 2. **EKONOMI / JIMAT**  
Susu ibu adalah percuma. Ianya tidak memerlukan wang untuk mendapatkannya.
- 3. **MENJARAKKAN KEHAMILAN**  
Pemberian susu ibu juga boleh mengelakkan kedudungan hasil ibu. Dengan ini kehamilan boleh dijarakkan.
- 4. **KASIH SAYANG**  
Semasa bayi disusui oleh ibunya, bayi tersebut merasa disayangi dan selamat dan ibu akan merasa lebih sayang kepada bayinya.
- 5. **ELAK BAHAR BUAH DADA / Ovari**  
Pemberian susu ibu boleh mengurangkan risiko buah dada dan ovari.
- 6. **PENGECUT RAHIM**  
Apabila bayi menyusu, rahim lebih cepat mengelut. Dengan ini perdarahan selpas bersalin dapat dielakkan.
- 7. **MELANGSINGKAN BADAN**  
Ibu-ibu yang menyusu bayi mereka dengan bantuan senaman dan makanan seimbang boleh membantu mengurangkan pengumpulan lemak di tempat-tempat tertentu seperti perut dan pinggang.

22

## Buku Harian Kangaroo Care

23

[figure not shown]

## Buku Harian Kangaroo Care

— Dokumentasi Jururawat & Ibu —

Umur Gestasi Minggu	Kangaroo Care				Berat Badan (kg)	Penyusuan	
	Pre Temp	Post Temp	Masa Mula	Masa Tamat		Jenis Penyusuan (✓)	
32/40					1.790 kg	Perahan Susu Badan	✓
Khamis 26/7/2018	36.8°C	37.2°C	8.00am	9.00am		Susu Badan	✓
Jumaat 2/7/2018	37.0°C	37.3°C	2.00pm	3.00pm	1.800 kg	Perahan Susu Badan	✓
						Susu Badan	✓
						Susu Formula	

24

## Appendix P : Slide Presentation KC-EP (Theory session)

United States Institute of Kangaroo Care

# KANGAROO CARE

1

Presented by :

## OBJECTIVES

1. Define premature infant and late preterm infant.
2. Explain the origins of Kangaroo Care (KC)
3. Define Kangaroo Care(KC).
4. Explain the different between Kangaroo Care(KC) and skin to skin contact.
5. State the different between Kangaroo Care(KC) and Kangaroo Mother Care(KMC)
6. State the indication and contraindication of Kangaroo Care(KC)
7. Explain the positioning safe for Kangaroo Care(KC).

2

## OBJECTIVES (CONT.)

8. State the benefit of Kangaroo Care(KC)
  - 8.1 For Infant
  - 8.2 For Mother
  - 8.3 For family
  - 8.4 For Institution
  - 8.5 For Nation
9. Explain how to document and follow- up policy for Kangaroo Care.

3

## Defining The Preterm Infant & Late Preterm Infant

- ❖ Preterm, preemies or premature infant refers to a baby born before 37 weeks of pregnancy have been completed.
- ❖ **Late Preterm Infant (LPI)** refers to 34 weeks/0 days to 36 weeks/6 days gestational age.

(WHO,2018)

4

## Classification Preterm By Weight

Table 1: Shows the classification of gestational age and weight

Classification of preterm	Gestational age	Classification of preterm infant	Weight
Overall preterm	< 37 weeks gestation	Low Birth Weight (LBW)	< 2500gram
Moderately preterm	Between 32 to 36+6(days) weeks gestation.	Very Low Birth Weight (VLBW)	< 1500gram
Very preterm	< 32 weeks gestation.	Extreme Low Birth Weight (ELBW)	< 1000grams

5

Bogota Nursery

Non-sterile IV  
bags; rinsed and  
reused

Shared Incubator;  
unreliable electricity  
source

Shared phototherapy

Infant in heating pad for  
warmth... NICU is 50°

Transitional Nursery...  
waiting for mom to KC

Mortality rate 70% infection

## The Origins Of Kangaroo Mother Care

- Kangaroo Mother Care was originated by **[name] and [name]** 1983 in Bogota, Colombia to reduce preemie mortality and morbidity..

9

## The Use Of Kangaroo Care Is Spreading Around The World

- It started in Bogota, Colombia approximately 30 years ago
- **Kmc in Africa** - Benin, Burkina Faso, Ethiopia, Mali and Malawi (WHO,2014)
- **Kmc in Asia** - India, Indonesia and the Philippines (Recent study,1990,2012)
- **KMC In Europe** - Belgium, Denmark, France, Italy, the Netherlands, Spain, Sweden and the UK (Spanish study report, 2013)

- Since 2011, "**Kangaroo Care Awareness Day**" has been observed worldwide on **May15**.

10

## Definition of Kangaroo Care

- ❖ It's a **special way** or method of **caring** for a **premature infant** in which the infant is position, skin-to-skin and **chest-to-chest (ventral surface)** contact from **umbilicus to sternum** of the infant is **upright** against the **mother's ventral surface**.
- ❖ Foster health, **weight gain**, promoting effective thermal control, **breastfeeding**, infection prevention and **bonding**.

Ludington-Hoe,et al.,(1990,2013,2018)

11

## Cont.

- **1 hour/60 minutes/day** to complete **one full cycle of sleep** and benefits of KC.
- < 30 minutes a day of KC no physiologic benefits.
- KC initiate in NICU & continue at home
- Continuously from **40 to 52 weeks post conception** (3 months old)

(Ludington-Hoe et.al., 2006,2010)

- Uninterrupted **60 minutes at first 12 w** continue **first 3 months** of life.

The Academy of Pediatrics US,(2013)

12

## Different Between Kangaroo Care(KC) & Skin To Skin Contact

### ❖ Kangaroo Care ....

- 1st KC is "**CHEST TO CHEST**" and skin to skin contact.
- 2nd KC is not "any" skin to skin contact.
- 3rd Skin to skin can be : cheek - to - cheek, head - to - breast and arm - in - hand **BUT** these position **Do Not Do** what the KC position **does !!**
- **2016**,June Chan et al.(2016) says SSC is most common part of KMC

13

[figure not shown]

Figure 1 : Structure of the lobes and inside the brain

14

## Different- Kangaroo Care from Skin To Skin Contact

- **Skin-to-skin contact** stimulates the brain through **A- AFFERENT NERVE**.
- Stimulation through **somatosensory cortex-source** of all common touch, pressure in the brain. (Left Amygdala)

[figure not shown]

Figure 2: Somatosensory cortex area

15

## Cont.

- **Kangaroo Care** stimulate the brain through an entirely separate set of nerves that are only responsive to **PLEASING TOUCH** and non-phasic stimulation of the chest, across the shoulders, stimulates the **C-AFFERENT** nerve. (Right Amygdala)
- Stimulation is through the **INSULAR CORTEX** of the LIMBIC brain.

[figure not shown]

Figure 3 : Insular cortex

16

## C- Afferents

- Message from **C-Afferents** goes directly to the **insular cortex**
  - limbic brain
  - seat of emotions and emotional memory

(Clausson HW et al.,2008. Unmyelinated tactile afferents have opposite effects on insular and somatosensory cortical processing)

17

## Neuropeptide Oxytocin Goes To Amygdala

- **Right Amygdala** is a center of **calm**,
- **contentedness, happiness, relaxation, compassion, empathy**,
- **sympathy** and ability to recognize a "safe", loving face.
- When infant **in KC**, nerve pathways to the right amygdala are set early and not undone later.

18

## Cont.

- **BUT**, when infant is **separated** from the mother, neuronal networks to **left amygdala** are established and **set within first three days** of life. (affect child's whole life)
- **Left Amygdala** is seat of **hatred, violence, aggression, fear, terror** and **inability** to determine if face is **safe or unsafe face**.

19

## Different Between Kangaroo Care(KC) & Kangaroo Mother Care (KMC)

### ❖ Kangaroo Care ....

- Skin-to-skin placement of the infant's chest against the chest of another human being – usually upright and chest-to-chest **(1-1.5 hours per day, at least 5 hours per week)**

### ❖ Kangaroo Mother Care...

- KC given by the mother, **continuously (24 hours/day x 7 days/week)** with unlimited access to the breast.

[name] (1991) Classified Glossary Of Terms & Breilbach (2001) Published In NANDA Nursing Diagnoses KC.

20

## Indication infants for Kangaroo Care

❖ **Indication** : GA >28 week or 30 week (corrected ages)

- Wt >1,000 –1,500 grams
- BW 1,300 –1,800 grams after **7 days old** weight 1,500 or less
- Wt > **than 1,500** grams with the combination :
  - Stable clinically :
    - HR**: 120 – 160 /min
    - RR**: 35 – 50 /min
    - SAo2** : 90 - 95%
    - Pink** color (good perfusion)

21

## Indication infants for Kangaroo Care(Cont.)

- Incubator / open air crib - can maintain (36.8 – 37.4 °C)
- Stable in low rate ventilator
- Dosages of medications have stabilized
- No O2 supplement or with low O2
- Consistently taking milk well.
- Gain weight (15 – 20 grams/day for 3 - 5 days/ 10 – 15 gram/day)
- Infant with phototherapy – Mother presses the fiber - optic blankets against the infant's back while doing KC.

22

## Contraindication For Kangaroo Care

### ❖ Infants.....

1. Wt <1000 g & < 28 week GA
2. Under radiant warmer – still quite sick
3. Umbilical artery catheter (UAC & UVC) - blocked
4. Chest tubes – dislodged during KC.
5. TPN – percutaneous line place in the arm- dislodged.
6. Scalp vein lvs, IVH grade 3 & 4 (bleeding into the brain) – too sick to participate in KC
7. Nil by mouth – may try to go to the breast during KC

23

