***a) Part I: Nurses' Perception of Kangaroo Care***

Part I assessed nurses' perception of KC related to their personal beliefs and the experiences that they had in the NICU. All twenty-five (25) items were adapted from the original KCQ tool developed by Arthur J. Angler & Eileen Brumbaugh, Ludington-Hoe et al. (2013), with slight modifications to meet the objectives of the study. A 5-point Likert response format was adopted. Descriptors were: strongly disagree (1) as the lowest score, followed by disagree (2), neither agree nor disagree (3), agree (4) and strongly agree (5); descriptor 5 was the highest score. With reference to the descriptors, the closer the score was to 5, the greater the appropriateness of the item. The items were positively and negatively worded (Appendix G). Positive items answered as 'strongly agree' or 'agree' were considered correct and if answered as 'strongly disagree', 'disagree' and 'neither agree nor disagree' were considered incorrect. The negative items were reversely rated. Out of 25 items there were 15 positive statements, which were (1,2,8,9,10,13,15,16,17,18,20,21,22,24,25), and 10 negative

statements, which were (3,4,5,6,7,11,12,14,19,23). The perception scores were converted into mean scores and then categorized into two groups. Mean scores of  $M=2.77$  and below indicated a high perception of KC, while mean scores above  $M=2.77$  indicated a low perception related to KC implementation. Therefore, mean scores of above 2.77 indicated less experience of KC with preterm infants in the NICU.

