**i) Contents Module Theory and Practical (8 hour)**

Module contents were organized to meet the objectives of this study. Purposes included the definition of KC, method of KC, benefits of KC, indication and contraindication of KC, guidelines and protocol for KC, recognized signs and symptoms of deterioration during and after the KC procedure, preparation of premature infant-mothers and equipment before, during and after the KC procedure, and showing how to record the infants' outcomes data for both groups in the KCPR booklet provided. The nurse should have been able to get a clear understanding of the programme and of the physiology and benefits of KC in detail and demonstrate the technique as well [Appendix P, Q(a)& Q(b)].

- 1) To define the term and amount of KC.
- 2) To explain the physiology and method of KC.
- 3) To state the benefits of KC to mother-infant dyads.
- 4) To state the indication and contraindication for kangaroo care and eligibility criteria for mothers and premature infants.
- 5) To state the guidelines and protocols before, during, and after the kangaroo care method.
- 6) To recognize signs and symptoms of deterioration among premature infants before, during , and after the method.
- 7) To state the preparation before, during and after the kangaroo care method
- 8) To list the equipment for kangaroo care method ;
  - 8.1 For infants
  - 8.2 For mothers
- 9) To educate and guide on recording in the KCPR booklet.
- 10) To demonstrate and return-demonstrate the KC method.

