### Part I : Perception on KC

No	Statement	5	4	3	2	1
1	All preterm babies should be allowed to participate in KC regardless of age.					
2	All preterm babies should be allowed to participate in KC regardless of weight.					
3	Babies receiving IV fluids should NOT be allowed to participate in KC.					
4	Babies who are intubated should NOT be allowed to participate in KC.					
5	Babies with umbilical catheters should NOT be allowed to participate in KC.					
6	Babies on ventilators should NOT be allowed to get KC.					
7	Babies with chest tubes should NOT be allowed to get KC.					
8	KC encourages the parenting role.					
9	KC enhances the attachment process between mother and baby.					
10	KC increases the quality of care on your unit.					
11	KC interrupts baby care\ giving.					
12	KC should be available only to breastfeeding mothers.					
13	KC is NOT feasible with some babies.					
14	KC keeps nurses too tied to the bedside.					
15	KC should be offered to all mothers in the NICU.					
16	KC will benefit preterm babies.					
17	KC will help mothers feel more confident in caring for their preterm baby.					
18	KC will improve the baby's outcome.					
19	KC will interfere with the completion of my tasks.					
20	Learning about KC will help me be a better nurse.					
21	Nurses look forward to introducing KC to a new mother.					
22	Our babies have adequate time for mother-baby contact without the use of KC.					
23	The increased amount of time required to prepare a baby for a KC session is out of proportion to the benefits.					
24	The teamwork required between nurses and mothers when doing KC is worth the effort.					
25	There is NOT enough flexibility in the NICU to allow parents extended visits (more than 1 hours) for KC.					

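### Two nurse perception items (a third on one reading) are scored opposite to the contraindications the nurse course teaches, and the 2.77 perception band contradicts the item key.

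*Combined protocol and SAP*

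**What the plan says.** **The course.** The nurse module in section 3.15 covers "indication and contraindication of KC, guidelines and protocol for KC", and stating the contraindications is one of its listed learning objectives. The Appendix P slide headed Contraindication For Kangaroo Care lists infants under 1000 g and under 28 weeks, "Umbilical artery catheter (UAC & UVC) - blocked" and "Chest tubes – dislodged during KC". The preceding indication slides also set a weight floor.

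**The perception scale.** Appendix H, Part I, item 2 reads "All preterm babies should be allowed to participate in KC regardless of weight". Item 7 begins "Babies with chest tubes should" and goes on to refuse them KC; item 5 does the same for umbilical catheters. Section 3.10.1, Part I, gives the key as "15 positive statements, which were (1,2,8,9,10,13,15,16,17,18,20,21,22,24,25" and, for the ten negative items, "statements, which were (3,4,5,6,7,11,12,14,19,23". Agreement with a positive item counts as correct and negative items are reversed. The 25 scores are averaged, and a mean of 2.77 "and below indicated a high perception of KC".

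**The knowledge scale.** Section 3.10.1, Part II, keys items 8 and 9 of the 20 knowledge items as true. These state that KC is contraindicated below 28 weeks and below 1000 g.

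**The analysis.** Table 3.4 analyses nurse perception through mean scores before and after the course. No item-level analysis is planned.

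**The concern.** The post-test comes about a week after a course that teaches these limits. On items 2 and 7 the taught answer is the one the key marks down. The questionnaire thus rewards the weight limit in its knowledge part and penalises it in its perception part. Perception is a named component of H3 (section 1.6). If the 25-item mean stays flat, a reader could not tell whether the course failed to change attitudes or whether some nurses learned the contraindications and lost points for it.

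The band adds a second problem. If it is applied as written, nurses with favourable keyed means are labelled as having low perception, so the categorised result reads in the opposite direction to the item scores.

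**Working it through.** **Check of the key.** The two lists hold 15 and 10 items, and together they cover items 1 to 25 once each. This reproduces the plan's 25 = 15 + 10. The keyed score is the response r (1 to 5) for a positive item and 6 − r for a negative item.

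**Scores at the two extremes.**

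| Item | Key | Accepts the taught limit | Rejects the taught limit |
|---|---|---|---|
| 2 (any weight) | positive | r = 1, score 1 | r = 5, score 5 |
| 7 (chest tubes) | negative | r = 5, score 6 − 5 = 1 | r = 1, score 6 − 1 = 5 |
| 5 (umbilical lines, conditional) | negative | r = 5, score 1 | r = 1, score 5 |

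The key separates the two nurses by 4 points per item, with the sign reversed relative to the course.

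Item 5 is conditional because the slide's note that a line is blocked can be read two ways. It may give the reason for the contraindication, as the dislodgement note does for chest tubes. It may instead limit the contraindication to lines already blocked, in which case there is no conflict. Item 1 (any age) is not counted, because it conflicts only if age means gestational age.

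**Gross effect on the 25-item mean.** Formula: number of items × points shifted ÷ 25. The shifts are assumptions; the documents give no item data.

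| Shift toward the taught answer | Items 2 and 7 | Items 2, 5 and 7 |
|---|---|---|
| 1 point | 2 × 1 / 25 = 0.08 | 3 × 1 / 25 = 0.12 |
| 2 points (neutral to full acceptance) | 2 × 2 / 25 = 0.16 | 3 × 2 / 25 = 0.24 |
| 4 points (extreme to extreme) | 2 × 4 / 25 = 0.32 | 3 × 4 / 25 = 0.48 |

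Offsetting the ceiling case needs a gain of 8 / 23 = 0.35 on each of the other 23 items, or 12 / 22 = 0.55 on each of the other 22. Nurses who already held the taught view at pretest would not move.

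**Items that can move the other way.** Items 4 and 6 (no KC if intubated or on a ventilator) are also reversed. The course presents an infant stable on a low-rate ventilator as suitable, and the transfer slides cover checking the endotracheal tube and draining ventilator tubing. Disagreement with items 4 and 6 after the course therefore raises the mean. Item 3 (IV fluids) may do so too, less cleanly, since scalp-vein lines are on the contraindication slide. Item 13 (KC not feasible for some infants) is keyed positive, so learning the limits raises it. As an illustration of sign only: if items 2, 5 and 7 each fall by one point and items 4, 6 and 13 each rise by one, the net is (3 − 3) / 25 = 0.

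**The band.** A nurse giving the most favourable keyed answer throughout has a mean of 5, above 2.77, and is labelled low perception. The least favourable mean, 1, is labelled high. This follows from the key and the band alone.

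**The case against.** The best defence is that Part I measures belief, and that facts about contraindications belong to Part II. A nurse may know a limit and still hold a generous attitude. That has some force, but section 3.10.1 itself calls perception answers correct or incorrect, which makes the conflict with the course one of scoring as well as construct.

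A second defence is size: two items of 25, in one nurse subscale, with a ceiling that needs every nurse to swing from one extreme to the other. That stands, and it keeps the point minor.

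A reader might go further than the documents allow in three ways.

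- **That learners and rejecters cannot be told apart on these items.** They can: the key separates them by up to 4 points per item, in the wrong direction. The signals mix only in the 25-item mean.
- **That the scale is biased against H3 overall.** Items 3, 4, 6 and 13 can move upward with the same course, so the net sign is not determined.
- **That item 13 is shown to be mis-keyed because mothers' item 8, the same statement, is reversed.** The mothers' reversed items 4, 5, 8, 17 and 19 correspond to nurse items 8, 9, 13, 22 and 24, all keyed positive. The mothers' form therefore gives no reason to reverse item 13 alone.

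**Conclusion.** The point holds as a minor scoring fault. Items 2 and 7 are keyed opposite to the course, and item 5 joins them if any umbilical line is meant. The slide joins weight and gestation with an ampersand, but reading it as requiring both limits does not rescue item 2, because weight would still exclude some infants.

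The gross effect is a lowering of the mean by 0.08 per one-point shift on both items (0.12 with item 5), with a ceiling of 0.32 (0.48). The net effect on H3 is unknown. There are no item-level data, no SD and no expected change for nurses against which to judge it. The band's contradiction of the item key is a separate fault and needs no assumption about how nurses answered. Neither fault bears on the infant primary outcomes.

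**What to change.** 1. State one scoring direction for nurse perception and make the 2.77 band agree with the item key, so that higher means are more favourable. Do this before classifying nurses or interpreting the pre-post change.
2. Keep the 25-item mean, as piloted in section 3.20.2, as the H3 perception outcome; do not re-key it.
3. Report items 2, 5 and 7 individually before and after the course.
4. Add a sensitivity mean without items 2 and 7 (23 items), and without item 5 as well (22 items). Say openly that under the item key this omission is expected to favour H3, because it removes items on which learning lowers the score.
5. As a secondary clinical clarification, have the clinical lead reconcile the slides. Points to settle are 1000 g for standing against 1500 g for sitting transfer, whether any umbilical line or only a blocked one is meant, and percutaneous lines, which are listed as a contraindication on one slide and checked for patency on the transfer slides.

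The cost is a wording change and a short re-run on existing questionnaires. The downside is a little more analysis, and the reduced score is not the piloted scale, so it should remain a sensitivity analysis.
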